must be completed before moving on to the next step, and steps much be completed in sequential order. During each step, your heart rate and sweating will be recorded via the electrodes on your chest and finger. After the experimenter reads the instructions for the next step and prior to completing the step, you will also be asked to rate your confidence level to complete the step on a scale from 0 to 100 (0= no confidence, 25= mild confidence, 50= moderate confidence, 75= high confidence, 100 = complete confidence) and your anticipatory distress on a scale from 0 to 100 (0=no distress, 25=mild distress, 50=moderate distress, 75= high distress, 100= severe distress). After completion of each step, you will be asked to rate your maximum level of distress during the step on a scale from 0 to 100. You are entitled to withdraw at any step if you do not wish to continue. Do you have any questions before we begin? The first step of the experiment is to stand 5 feet away from the tarantula while it is in its closed container for 30 seconds. The final step of the experiment is to touch the back of the tarantula's leg with the tip of your index finger continuously for 30 seconds." Before beginning the BAT and after ensuring comprehension of the above instructions, the experimenter will ask the participant to rate his/her overall confidence and overall anticipatory distress with respect to his/her ability to complete all nine steps (see rating scales in above instructions). Before each subsequent step, the participant will be asked to rate his/her confidence and anticipatory distress regarding his/her ability to complete that particular step. During each step, the experimenter will record the spider's movement on a categorical scale (0 = no movement, 1 = a little movement, 2 = a lot of movement). After each step, the participant will be asked to rate his/her maximum level of distress while completing that particular step. Finally, the experimenter will record the number of steps willingly completed for a given participant.

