This visit will occur five to seven days after Day 3. All participants will complete the Spider Phobia Questionnaire (SPQ; Klorman et al, 1974) and Fear of Spiders Questionnaire (FSQ; Szymanski & O'Donohue, 1995), uploaded in Section 10.1, Item 1.0, to test for change in arachnophobia fear/avoidance symptoms as a function of TMS treatment received. Next, all participants will complete an identical BAT to that completed at their first visit with the same tarantula (see DAY 1 above). Self-report and physiological (i.e., SCR) data will again be collected. After completion of these forms, participants will be debriefed by an un-blinded member of the study team and informed to which group they are assigned. They will be

encouraged to discuss whatever questions or concerns they have regarding the study at that time.

After completion of Day 4, participants will be compensated for their time with one credit per hour of study participation.

Dependent variables (DVs) will be quantitative self-reports and behavioral symptoms of fear and avoidance of spiders both pre- and post-treatment, including SCR (difference between baseline and average level during BAT anticipation period, and number of peaks during BAT), total number of steps completed during the BAT, self-reported distress, anticipatory distress, and maximum distress per BAT step, and total score on the SPQ. BAT measures will be collected for each step and therefore minima, maxima, and means will be compared between the two groups. Primary outcomes examined will be number of steps completed during BAT, self-reported distress during BAT, number of SCR peaks during BAT, SPQ score, and FOS score. All other variables examined will be secondary outcomes. Additionally, for feasibility and tolerability assessment, attendance to TMS treatment sessions and early termination of TMS treatment sessions will be recorded. The primary independent variable examined will be the treatment group (iTBS vs. control iTBS). The sample size will be 40 participants (20 per group). Pre-comparison ANOVA will be performed to limit type 1 error due to multiplicity of comparisons.

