Hypotheses will be tested using between-group two-tailed t-tests given that we are testing not only for magnitude of an effect, but also direction of an effect. We expect that comparisons of efficacy will demonstrate increased confidence during BAT approach, decreased endorsed fear of spiders as measured by SPQ and FSQ, and reduced physiologic response to stimulus (reduced HRV and SCR) with active iTBS and exposure when compared to control iTBS and exposure. We expect that comparisons of feasibility and tolerability will show no significant difference between attendance to, early termination of, or subjective tolerability ratings of TMS treatment sessions between treatment groups.

NOTE 2/2/21: the above reported statistical analysis plan was modified given the small sample size, technical limitations, and distributions of the data observed. The number of statistical tests performed was minimized and multi-level mixed-effects models (MLMs) and nonparametric tests were utilized as appropriate based on the sample size of the experiment. Behavioral measures acquired during the BATs (anticipatory distress, maximum distress, mean skin conductance at each step) were examined using MLMs in Stata version 16.1 as functions of BAT step, group assignment, and timepoint (pre or post-treatment). All other analyses were performed in SPSS (version 26.0.0.0). Demographics and experimental parameters were analyzed for between-group differences using 2-sided Mann-Whitney U Tests. Changes in self-reported fear of spiders (SPQ and FOS) were analyzed using a repeated-measures MANOVA (Greenhouse Geisser correction was applied in case of non-sphericity). A pair of chi-square analyses were performed to validate blinding of the study (based on questionnaires completed by subjects and raters), and no significant deviation from 50/50 chance was observed. A p-value of <0.05 was considered significant for all testing.

ADVERSE EVENT MANAGEMENT

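### The undefined pre-comparison ANOVA gives at most weak type 1 error control across five unranked primaries, and the 2/2/21 note names no adjustment

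*Combined protocol and SAP*

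**What the plan says.** The DAY 4 section of the combined protocol and SAP names as primary "number of steps completed during BAT, self-reported distress during BAT, number of SCR peaks during BAT, SPQ score, and FOS score" and makes every other variable secondary. It gives no order among the five and no rule for what counts as success. Its one provision for multiplicity is "Pre-comparison ANOVA will be performed to limit type 1 error due to multiplicity of comparisons". The plan then continues: "Hypotheses will be tested using between-group two-tailed t-tests". No significance level is given at this point. The same section says that each BAT measure will be compared between groups by its minimum, maximum and mean.

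The list of dependent variables separates "self-reported distress, anticipatory distress, and maximum distress per BAT step" and does not say which of these is the distress primary. The BAT instructions under DAY 1 collect two distress ratings per step. One comes beforehand ("Before each subsequent step, the participant will be asked to rate his/her confidence and anticipatory distress regarding his/her ability to complete that particular step") and one after completion ("you will be asked to rate your maximum level of distress during the step on a scale from 0 to 100").

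The note dated 2/2/21 says "the above reported statistical analysis plan was modified given the small sample size, technical limitations, and distributions of the data observed", and adds "The number of statistical tests performed was minimized". It names these analyses:

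- mixed models for anticipatory distress, maximum distress and mean skin conductance, with step, arm and pre/post timepoint as predictors;
- one repeated-measures MANOVA for SPQ and FOS;
- Mann-Whitney tests for demographics and experimental parameters;
- two chi-square tests of blinding.

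The note sets 0.05 as the threshold for every test, which is the only significance level in the document. It mentions neither the ANOVA nor any adjustment.

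**The concern.** The plan claims a protection against multiplicity but does not describe it well enough to be checked. With five unranked primaries and no success rule, a reader cannot tell which result decides the question or how often a chance finding would appear among them. The note was written in the light of observed data and does not settle this. It leaves open whether the ANOVA was run, which distress rating is primary, and which group term in the mixed models is the treatment test. It also names no analysis for two declared primaries, BAT steps completed and number of SCR peaks; mean skin conductance is a different measure.

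The Background section presents the study as a way to gather preliminary data, so no treatment decision hangs on it. What is at stake is interpretation: one result below 0.05, among several that were not ranked in advance, could be taken as evidence of efficacy and carried forward as such.

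**Working it through.** The plan states no familywise error rate, and no effect size or power for its 40 participants, so there is no figure of its own to reproduce.

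**Inputs from the document.** Five primaries, two arms, 20 per arm and two-sided tests (DAY 4 and the hypotheses paragraph that follows); level 0.05 (2/2/21 note only). **Assumptions.** Normal outcomes with a common correlation of 0 to 0.9; where one outcome is truly affected, an effect of 1.0 or 1.5 SD.

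**1. ANOVA run separately on each outcome.** With two arms and 20 + 20 − 2 = 38 degrees of freedom, F(1, 38) = t(38)². The two p-values are the same; over 2,000 simulated data sets the largest difference was 6e-16. Such a gate removes no false positives.

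**2. ANOVA over steps or timepoints within one BAT measure.** This could limit the comparisons made inside that measure. It does not act across the five outcomes.

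**3. One omnibus test over all five outcomes, then t-tests at 0.05.** This is the most favourable reading. It was simulated as a Hotelling T² gate at 0.05 with 20 per arm. The entries are the percentage of trials with at least one false positive:

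| Assumed correlation | 0 | 0.3 | 0.5 | 0.7 | 0.9 |
|---|---|---|---|---|---|
| No outcome affected | 4.7 | 4.2 | 3.7 | 3.2 | 2.2 |
| One affected (1.0 SD), error among other four | 15.4 | 15.4 | 15.0 | 13.1 | 9.4 |
| One affected (1.5 SD), error among other four | 18.0 | 17.2 | 15.7 | 13.3 | 9.5 |

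This is weak control. It holds under the global null and is lost for the remaining outcomes once one effect is real.

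**4. The note's analyses of primaries.** These are the SPQ/FOS MANOVA plus one distress model (k = 2) or both (k = 3). Suppose that each yields one treatment p-value and that any p < 0.05 would be read as efficacy. Under independence the chance of at least one false positive is 1 − 0.95^k:

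- k = 2: 1 − 0.9025 = 9.75%
- k = 3: 1 − 0.857375 = 14.3%

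The simulated values, with t-tests standing in for the note's models (100,000 runs), are:

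| Assumed correlation | 0 | 0.3 | 0.5 | 0.7 | 0.9 |
|---|---|---|---|---|---|
| k = 2 (%) | 9.6 | 9.5 | 9.2 | 8.5 | 7.0 |
| k = 3 (%) | 14.1 | 13.5 | 12.7 | 11.0 | 8.5 |

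These are not ceilings. If two group terms (group-by-time and group-by-time-by-step) were read from each distress model, the counts become 1 + 2 = 3 and 1 + 4 = 5, giving 14.3% and 1 − 0.95^5 = 22.6% under independence.

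**5. Cost of an adjustment.** Holm over five starts at 0.05/5 = 0.01. From the noncentral t with 20 per arm, the effect detectable with 80% power rises from d = 0.91 at 0.05 to d = 1.13 at 0.01. Power at d = 0.91 falls from 80% to 57%.

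**The case against.** The strongest reply is that this is a small pilot, that formal familywise control is not expected of it, and that the note already cut the number of tests and took SPQ and FOS together. Much of that stands. The reduction is real, and it is why the working counts two or three analyses, not five. But running fewer tests is not an adjustment. The MANOVA joins only two of the five primaries, and its Greenhouse-Geisser correction deals with sphericity, not multiplicity. A pilot need not control familywise error, but it should not claim a control that it does not have.

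Four stronger readings are tempting, and the documents do not support them:

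- **That the ANOVA claim is still in force.** The note says the plan above it was modified and does not say whether the ANOVA went with the t-tests. Its status is unclear.
- **That the ANOVA gives no protection at all.** An omnibus version would hold error at 2-5% when no outcome is affected. Only the study team knows what was intended or run.
- **That two primaries were dropped.** The note's general wording on nonparametric tests and on remaining analyses done in SPSS might cover BAT steps and SCR peaks. It does not say so.
- **That the distress primary could be any of the ratings.** The maximum rating refers to distress felt in the step and the anticipatory rating precedes it, so maximum distress is the natural reading of distress in the BAT. The dependent-variable list, which names the terms separately, still leaves this to be confirmed.

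**Conclusion.** The concern holds. The plan claims to limit type 1 error by a step that it does not define, and none of the three plausible readings gives strong control across the five primaries. The note applies 0.05 to every test, names no adjustment and does not clear up the ANOVA.

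The size is about 7-10% for two primary analyses and 8-14% for three. This is illustrative. It assumes one treatment p-value per analysis, correlation between 0 and 0.9, and a reader who takes any single significant primary as efficacy, a rule that the documents do not state. A reader might infer that the trial's error rate is 22.6%, the figure for five independent tests. No single figure is the study's error rate, because the number of tests, the terms used and the correlations are not given. At every correlation examined, two or three unadjusted analyses exceed 5%.

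The point should be fixed, but its consequence is limited to how the pilot's results are read.

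**What to change.** Leave the existing text as the record of what was planned and done, and add a dated clarification that:

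- (a) says whether and how the pre-comparison ANOVA was run, and that it gives at most weak control and is not relied on for error control across the five primaries;
- (b) labels 0.05 as a nominal, unadjusted level and the efficacy results as exploratory, with no single one taken as evidence of efficacy;
- (c) states which distress rating is the primary and that group-by-time is the treatment term, and discloses if either was chosen after data were seen;
- (d) reports between-group estimates with 95% confidence intervals for all five declared primaries, or the technical reason why one could not be analysed.

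Only if a significance claim on the primaries is kept: report Holm-adjusted p-values across the five, with one p-value each (SPQ and FOS separately), keep an unanalysable primary in the family as p = 1, and disclose that the method was chosen post hoc. In simulation with 20 per arm, Holm held the familywise error at or below 5%, both with no outcome affected and among the other four with one affected.

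The exploratory route costs a paragraph and five estimates, and no new data if the step counts and skin conductance recordings are usable. Its price is that no unadjusted efficacy significance claim can be made. The Holm route costs the power shown in the working. The note does not state how small the final sample was; at an assumed 15 per arm the detectable effect would rise from d = 1.06 to 1.33, and at an assumed 10 per arm from 1.33 to 1.69.

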Treatment of specific phobias, a disproportionate conditioned fear to a specific stimulus, typically involves exposure therapy, an extinction-based behavioral technique employed in the context of cognitive behavioral therapy (CBT). (Loerinc et al., 2015; Pachana, Woodward, & Byrne, 2007; Wolitzky-Taylor, Horowitz, Powers, & Telch, 2008) It involves exposing an individual to his or her feared stimulus in an effort to generate new non-fear associations with that stimulus. Treatment benefit with exposure therapy is observed in 70-75% of individuals compared to placebo. (Wolitzky-Taylor et al., 2008) However, not only do 25-30% of individuals not respond to exposure therapy, but few studies examining exposure therapy report long-term outcomes.(Wolitzky-Taylor et al., 2008) And these phobias are estimate to affect up to 15% of the world's population. (Eaton, Bienvenu, & Miloyan, 2018; Wolitzky-Taylor et al., 2008) In the cases where therapy fails or a patient would prefer medication, a low-dose benzodiazepine can be used, though it is not considered first-line. (Pachana et al., 2007; Wolitzky-Taylor et al., 2008) This project is designed to examine the feasibility of combining exposure therapy and iTBS treatment for phobia, and gather preliminary data to address the question of whether this combination might lead to greater or more rapid symptom resolution than exposure alone. Should our hypothesis prove true, further study may yield a new effective treatment for phobias. This would not only impact the treatment of phobias, but provide the first evidence for the usefulness of iTBS in an integrated treatment approach for phobia.

OVERVIEW

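### Feasibility of exposure plus iTBS is an aim, but its only stated analysis is a between-arm comparison expected to be null, which cannot show feasibility; non-significance likewise shows neither similar tolerability nor a secure blind

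*Combined protocol and SAP*

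**What the plan says.** Background and significance gives the aim: "This project is designed to examine the feasibility of combining exposure therapy and iTBS treatment for phobia", alongside gathering preliminary data on efficacy. The DAY 4 outcomes paragraph says that, for feasibility and tolerability, "attendance to TMS treatment sessions and early termination of TMS treatment sessions will be recorded". It plans 40 participants, 20 per group.

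The next paragraph gives the one analytic statement on these measures: "We expect that comparisons of feasibility and tolerability will show no significant difference between attendance to, early termination of, or subjective tolerability ratings" of TMS sessions between treatment groups. The efficacy sentence just before it describes the arms: "with active iTBS and exposure when compared to control iTBS and exposure". The DAY 1 text confirms that control iTBS uses the same stimulation parameters at another site (the vertex).

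No target attendance or completion rate, acceptable termination rate, interval or margin is given.

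The NOTE of 2/2/21 says the analysis plan was modified. It does not name attendance, early termination or tolerability. The nearest statement is "Demographics and experimental parameters were analyzed for between-group differences using 2-sided Mann-Whitney U Tests", which may or may not include them. On blinding it reports "A pair of chi-square analyses were performed to validate blinding of the study", based on questionnaires from subjects and raters, and that "no significant deviation from 50/50 chance was observed".

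**The concern.** The feasibility question is whether participants attend and complete exposure plus iTBS. That is a question about absolute rates. A comparison between two arms that both receive the combination has no reference point for it: equally good and equally poor attendance both give a null result, at any sample size.

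For tolerability the between-arm comparison is relevant, because the arms differ in stimulation site. A non-significant result from 20 per arm, however, is weak evidence of similarity.

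The same reasoning applies to the blind. Failing to reject 50/50 is offered as validation, yet a small number of guesses would often miss moderate unblinding. This matters because at least four of the five primary outcomes are open to expectation: BAT distress, SPQ and the Fear of Spiders score are self-reported, and BAT steps are those the participant is willing to complete.

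**Working it through.** **Inputs.** From the DAY 4 text: 20 per arm and two-sided between-group t-tests. From the NOTE: significance at p < 0.05, and a pair of chi-square tests against 50/50. The documents give no attendance, termination or guess counts, so every count below is an illustration. The sample size comes with no power, effect size or margin, so there is no figure of the plan's own to reproduce.

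**1. Feasibility.** Compare two situations under the same between-arm test.
- 12/20 complete in each arm: difference 0, p = 1.0. Pooled 24/40 = 60%. Clopper-Pearson 95% limits are the 2.5% quantile of Beta(24, 17) = 0.433 and the 97.5% quantile of Beta(25, 16) = 0.751, so 43 to 75%.
- 19/20 complete in each arm: difference 0, p = 1.0. Pooled 38/40 = 95%, exact 95% CI 83 to 99%.

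The p-value is identical and the feasibility message is opposite. By exact enumeration of the t-test on 0/1 data, if the true rate is 50% or 60% in both arms, the result is non-significant 96% or 95% of the time. More participants would not change this.

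**2. Tolerability.** Early termination is taken as one yes/no per participant (an assumption).
- 5/20 versus 1/20: sample variances 0.1974 and 0.0500, pooled 0.1237; SE = sqrt(0.1237 × 2/20) = 0.111; t = 0.20/0.111 = 1.80 on 38 df; p = 0.080. The Newcombe 95% CI for the difference is -3 to +42 points. A Mann-Whitney test on the same counts gives p = 0.084, so the NOTE's move to nonparametric tests would not alter the reading.
- 2/20 versus 2/20: Wilson limits for each arm are 0.028 and 0.301. Newcombe half-width = sqrt((0.100 - 0.028)² + (0.301 - 0.100)²) = 0.214. Identical observed rates still leave about -21 to +21 points.
- Exact power for a true 25% versus 5% is 44%.
- For a rating scale, the 95% CI half-width is 2.024 × sqrt(2/20) = 0.64 SD.

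**3. Blinding.** Assume a one-sample chi-square on n guesses: (x - n/2)²/(n/4) > 3.84. With n = 40, x = 26 gives 3.6 (not rejected) and x = 27 gives 4.9 (rejected), so rejection on the upper side needs 27 or more correct. Exact binomial power:

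| True correct rate | 40 guesses | 30 guesses | 20 guesses |
|---|---|---|---|
| 60% | 21% | 18% | 13% |
| 65% | 44% | 36% | 25% |
| 70% | 70% | 59% | 42% |
| 75% | 90% | 80% | 62% |

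Even exactly 20/40 correct leaves a Wilson 95% CI of 35 to 65%. A null from about 40 guesses therefore argues against gross unblinding but leaves moderate unblinding open.

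**The case against.** The text says what the investigators expect. It does not declare that p > 0.05 will count as proof of feasibility, and a reader who infers such a success criterion goes beyond the documents. Attendance and early termination are recorded, so absolute rates can be reported. The between-arm comparison is not idle, since it asks whether the active site costs attendance or comfort relative to the vertex. All of this stands. What remains is that no other analysis or yardstick is given for a stated aim, and this one cannot answer it.

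The 60% illustration may be far from what occurred. The OVERVIEW section limits enrolment to people able to complete all four visits, which favours high attendance. That also stands: the example makes a logical point and is no forecast. The same restriction limits how far a high observed rate can be generalised.

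This is a small pilot, and low power for secondary contrasts is expected. True, but rates with intervals need no power, and feasibility is a natural aim for a pilot.

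On blinding, a reader might infer that the blind failed, or that a difference between arms was hidden by pooling. The documents support neither. They do not say how the chi-square tables were laid out. They also point both ways on sensation: the vertex is described as causing less scalp discomfort, but as having a risk profile similar to other sites, and people with previous TMS treatment are excluded. The missing guess counts are a reporting gap, not evidence of a wrong analysis.

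**Conclusion.** The concern holds in a limited form. For feasibility it is a matter of logic and rests on no assumed number: both arms receive the combination, so their similarity says nothing about whether it can be delivered. For tolerability and blinding it is a matter of precision. At 20 per arm, differences of around 20 percentage points in early termination remain open. With an assumed 20 to 40 guesses, a true correct-guess rate of 60 to 65% would be missed more often than not.

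These sizes assume the planned sample, one yes/no termination outcome per participant and a one-sample test of guesses. The achieved numbers are not given; smaller ones would widen the uncertainty.

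It would be too strong to say that feasibility cannot be assessed from this trial, since the data were to be recorded, or that the NOTE dropped the feasibility analysis, since its wording is unclear on that. This is a minor-to-moderate analysis and reporting correction.

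**What to change.** - Report attendance, session completion and early termination per arm and pooled, with exact 95% CIs, and the between-arm difference with its 95% CI.
- Base feasibility statements on the rates and tolerability statements on the intervals, not on p > 0.05. State the enrolment restriction beside the attendance rates. Label any feasibility threshold set now as post hoc.
- State in the NOTE which analysis was applied to these measures.
- Report the subjective tolerability ratings if they were collected. They appear in the expectation but not in the DAY 1 questionnaire list or the DAY 4 outcomes paragraph. If they were not collected, drop that comparison.
- Replace the claim that the chi-square tests validated the blind with correct-guess rates by arm, numbers of guesses and 95% CIs, for subjects and raters separately.

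The cost is rewording and simple intervals on data already collected. The downside is that the tolerability and blinding statements become less favourable.

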The experiment will consist of four days. Day 1 will include informed consent, questionnaires, a behavioral approach test with a spider, a series of short exposures with a spider, and the first TMS treatment (for a total of approximately 75-90 minutes). Day 2 will occur one to two days after Day 1 and will consist of a second series of short exposures with a spider and the second TMS treatment (30 minutes). Day 3 will occur one to two days after Day 2 and will also consist of a series of short exposures and a TMS treatment (30 minutes). Day 4 will occur five to seven days after Day 3 and will consist of post-study questionnaires and an identical behavioral approach test as is conducted on the first visit (30 minutes). Participants will be randomized to either an active TMS treatment group (using an iTBS stimulation protocol over the participant's ventro-medial prefrontal cortex, an area involved in phobic response) or a control TMS treatment group (using the same iTBS stimulation protocol over the central sulcus and between hemispheres, a site not associated with memory or fear response).

Prospective participants will be undergraduate students recruited through the UCLA Psychology Department Subject Pool (i.e., SONA). At this time, this small pilot study is not equipped to recruit from the population at-large, and therefore is currently limited to recruitment through SONA. All prospective participants will be screened with the 31-question Spider Phobia Questionnaire (SPQ) to ensure eligibility for participation, with a minimum total score equal to or greater than 17 required for participation.(Klorman, Weerts, Hastings, Melamed, & Lang, 1974) Participants will be enrolled for the study only if they are able to complete all four visits of the experiment. Exclusion criteria will include:

1) Subject is mentally or legally incapacitated, unable to give informed consent.

- 2) Subjects with psychosis (psychotic depression, schizophrenia, or schizoaffective diagnoses (lifetime)); bipolar disorder (lifetime); dementia (lifetime); delirium within the past 6 months; eating disorder within the past year; obsessive-compulsive disorder (lifetime); post-traumatic stress disorder within the past year; acute risk for suicide or self-injurious behavior. Patients with diagnostic uncertainty or ambiguity (e.g. rule-out pseudodementia of depression) will be excluded.

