Participants will be assigned course credit after participating in the study. Participants will sign up for the study only if they are able to make all four visits of the experiment. If a participant does not attend all three visits, course credit will still be given for the amount of time the participant spent doing the experiment (i.e., 1 credit for 1 hour). At this time, participants will be emailed blank copies of the forms, questionnaires, and screening tools that will be completed during the first visit, and they will be informed that they may complete the forms in advance and bring the completed forms with them to save time, should they desire. They will be asked to not return their forms via email, and to only bring them to the first visit.

DAY 1

On Day 1, participants will first provide informed consent after the nature of the study has been fully explained and the participant has had time to ask questions. After obtaining informed

consent, participants will complete a demographics and eligibility questionnaire (see Section 10.1, Item 1.0) or hand in their already-completed forms, which will be reviewed by the researcher upon completion. Ineligible participants (i.e., participants with bee, insect, or spider allergies, with scores below 17 on the SPQ, who do not speak English, are taking medications that lower the seizure threshold, or other exclusion criteria as listed in section 11.1) will be informed that they do not meet criteria and the research session will be terminated at this time. Participants found to be ineligible will still receive 1 credit for their time. All to-beadministered questionnaires are listed below and uploaded in Section 10.1, Item 1.0 of this IRB submission.

Spider Phobia Questionnaire (SPQ; Klorman et al, 1974)
Demographics & Eligibility Questionnaire
Fear of Spiders Questionnaire (FSQ; Szymanski & O'Donohue, 1995)
PHQ2
PHQ9
Hamilton Rating Scale for Depression (specifically the suicidality item)
GAD7

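### SPQ and FOS are compared as change scores with no Day 1 covariate: valid, but it probably costs some precision for FOS, by an amount the documents do not let us fix.

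*Combined protocol and SAP*

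**What the plan says.** The Project Summary plans to compare pre-to-post changes between the two groups. The DAY 4 section lists SPQ score and FOS score among the primary outcomes and plans 40 participants, 20 per group.

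The note of 2/2/21 replaces the planned t-tests and explains that "the above reported statistical analysis plan was modified given the small sample size, technical limitations, and distributions of the data observed". For the two questionnaires it reports: "Changes in self-reported fear of spiders (SPQ and FOS) were analyzed using a repeated-measures MANOVA". For anticipatory distress, maximum distress and mean skin conductance during the BAT it reports mixed models fitted "as functions of BAT step, group assignment, and timepoint (pre or post-treatment". Neither sentence names a Day 1 covariate or an interaction term. The note adds: "The number of statistical tests performed was minimized".

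Two design features bear on the point. Entry depends on SPQ, with a "minimum total score equal to or greater than 17 required for participation" (OVERVIEW), and people "with scores below 17 on the SPQ" are turned away on Day 1. In the BAT, each step "must be completed before moving on to the next step, and steps much be completed in sequential order", and participants are told: "You are entitled to withdraw at any step if you do not wish to continue".

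**The concern.** SPQ and FOS are each measured once before and once after treatment. The group effect on change is then the difference between arms in mean (Day 4 minus Day 1), which fixes the slope of Day 4 on Day 1 at 1. Adjusting for the Day 1 value estimates that slope from the data. When the true slope is below 1, as it usually is for a noisy scale, the change score carries Day 1 noise into the estimate and the interval is wider than it need be.

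This small pilot was set up to gather preliminary data. Its main product is an effect estimate and interval for planning the next study, so avoidable width in a primary outcome is worth removing when the Day 1 values are already in hand.

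**Working it through.** **Nothing to reproduce.** The sample size of 40 comes without power, effect size, SD or correlation.

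**Inputs from the documents:** 20 per group planned; entry at SPQ of 17 or more; one Day 1 and one Day 4 value per scale.

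**Assumptions, none in the documents:**
- FOS is the Fear of Spiders Questionnaire, elsewhere abbreviated FSQ.
- r is the pre-post correlation before selection on SPQ: 0.3 to 0.8.
- Scores are bivariate normal before selection.
- The cut keeps the top 10-30% of SPQ scores, and SPQ and FOS correlate 0.5 to 0.8. With an SD of 1 before selection, the Day 1 SD after selection (s) is then 0.68-0.90 for FOS and 0.41-0.51 for SPQ.
- The Day 4 SD before selection is m times the Day 1 SD; m = 1 unless stated.
- The analysed number is 10 to 20 per arm (n), since the note does not give it.

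**Formulas.** Write Day 4 = m(rB + √(1−r²)e), where B is the Day 1 value and e is independent with SD 1. Per participant:
- change-score variance = (mr−1)²s² + m²(1−r²)
- adjusted variance = m²(1−r²) × [1 + 1/(2n−4)], where the bracket is the cost of estimating the slope: 1.028 at n = 20 and 1.0625 at n = 10

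For m = 1 the variance ratio, change over adjusted, is [1 + s²(1−r)/(1+r)] / [1 + 1/(2n−4)]. The width ratio is its square root times the ratio of t quantiles: 2.024/2.026 = 0.999 at n = 20 and 2.101/2.110 = 0.996 at n = 10.

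**FOS, the two ends of the range for r = 0.3 to 0.5.**
- r = 0.3, s = 0.90, n = 20: (1 + 0.81 × 0.538)/1.028 = 1.397; √1.397 × 0.999 = 1.18.
- r = 0.5, s = 0.68, n = 10: (1 + 0.462 × 0.333)/1.0625 = 1.086; √1.086 × 0.996 = 1.04.

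FOS interval width, change score relative to adjusted:

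| r | 20 per arm | 10 per arm |
|---|---|---|
| 0.3 | 1.10-1.18 | 1.08-1.16 |
| 0.5 | 1.06-1.11 | 1.04-1.09 |
| 0.7 | 1.03-1.05 | 1.01-1.03 |
| 0.8 | 1.01-1.03 | 0.99-1.01 |

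A simulation of 40,000 trials per cell gave width ratios, adjusted over change, of 0.85-0.96 for r = 0.3 to 0.5. Inverted, 1/0.96 = 1.04 and 1/0.85 = 1.18, so the two methods agree.

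**FOS when the SDs differ (r = 0.5).**
- m = 0.8: change-score interval 14-25% wider at 20 per arm.
- m = 1.25: 1-3% wider at 20 per arm; from about 1% narrower to 1% wider at 10.
- m = 1.5: no gain from adjusting at 20 per arm; the adjusted interval is 2-3% wider at 10.

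So r alone does not bound the gain, and in unfavourable cases its sign changes.

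**SPQ.** With s = 0.41-0.51 and m = 1, the same formula gives a change-score interval 1-5% wider at 20 per arm for r = 0.3 to 0.5. At 10 per arm it runs from 1% narrower to 3% wider. At r = 0.7 to 0.8 and 10 per arm, adjusting makes the interval 1-3% wider.

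**The case against.** The strongest reply is that this is an efficiency preference. Change scores are unbiased under randomisation, pre-to-post change is the comparison the Project Summary asks for, and Day 1 values are already used as one of the repeated outcomes. The unknown SD ratio can erase the gain, the analyses are done, and the note deliberately kept the number of tests down. All of that stands. It limits the point to precision and the remedy to labelled estimates. It does not remove the case for showing an estimate that usually has a narrower interval and needs no new data.

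A reader might infer three stronger things, none of which the documents support:

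- **That the BAT models omitted group-by-timepoint.** A model with main effects only would average Day 1 with Day 4 and, with equal numbers of steps on both days, recover half of a Day 4 effect. No sentence says such a model was fitted. The note lists factors rather than a formula, and the Project Summary and DAY 4 section make the interaction the natural reading. The unlisted terms are missing detail. The MANOVA sentence does not name its group-by-time term either, and both sentences deserve the same reading.
- **That chance Day 1 imbalance is a second harm.** A difference above 0.5 SD has probability 2[1 − Φ(0.5/√(2/n))], which is 11% at 20 per arm and 26% at 10, and the change score then moves the estimate the opposite way. But averaged over trials, that movement is exactly the (mr−1)²s² term in the variance above. Counting it again would double the same loss.
- **That the results are biased or that baseline was ignored.** Neither is so.

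**Conclusion.** The point holds as a modest, conditional loss of precision, mainly for FOS. The 4-18% rests on r of 0.3 to 0.5, equal SDs before selection, 10 to 20 analysed per arm, and the selection assumptions listed. At r = 0.7 to 0.8 the loss is about 5% or less. A smaller Day 4 SD makes it larger; a Day 4 SD about 1.5 times larger, or high r with about 10 per arm, removes or slightly reverses it. For SPQ little or nothing is at stake. Confidence is medium, because every quantity that sets the size is assumed. The trial's own Day 1 and Day 4 data would settle it at once.

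**What to change.** Beside the MANOVA, report the Day 4 FOS group difference adjusted for Day 1 FOS, with a 95% confidence interval. Do the same for SPQ, for consistency. State the number analysed in each arm.

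For the three BAT mixed models, list the terms. As the same kind of sensitivity estimate, report the Day 4 group difference from a group-by-timepoint model with a common Day 1 mean (no separate group effect at Day 1). Participant-level random intercepts and timepoint effects are the natural start; use simpler random effects if the model does not converge, which is possible at this size. Avoid a per-step Day 1 covariate: steps are sequential and participants may stop, so it would be missing for every step not reached on Day 1.

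Label all of these as post hoc sensitivity estimates and not as further tests at 0.05, because the plan was changed after the data were seen and the number of tests was deliberately limited.

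Cost: one degree of freedom per scale, a possible slight loss of precision for SPQ, refitting three models, and a few sentences. No new data are needed.
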